However, hybrid therapy requires additional two antibiotics in the last 7 days, which can confuse patients and may dampen enthusiasm for its use. Reversing the sequence of drug administration (a quadruple regimen followed by a dual regimen) can simplify hybrid therapy. The aims of this randomized controlled trial are (1) to compare the efficacies of reverse hybrid therapy and bismuth quadruple therapy, (2) to investigate the host and bacterial factors predicting the treatment outcomes of the two eradication regimens.

PATIENTS & METHODS

Study population

The open-labeled trial is conducted at the Kaohsiung Veterans General Hospital and Kaohsiung Medical University Hospital in Taiwan in accordance with the principles of good clinical practice from the Declaration of Helsinki. The study protocol will be approved by the Ethics Committees of the Kaohsiung Veterans General Hospital and the Kaohsiung Medical University Hospital. All patients give written informed consent before participating in the study.

We will recruit 352 patients to the study if they meet the following criteria: they are adult patients aged ≥ 20 years and have *H pylori* infection. The exclusion criteria include The exclusion criteria include (1) previous *H pylori*-eradication therapy, (2) patient with allergic history to the medications used, (3) patients with previous gastric surgery, (4) coexistence of serious concomitant illness (for example, decompensated liver cirrhosis, uremia), and (5) pregnant

women.

Randomization and treatment

This is a randomized controlled trial. Eligible *H. pylori*-infected subjects are randomly assigned to a 14-day reverse hybrid therapy (a 7-day quadruple regimen with pantoprazole 40 mg twice daily, amoxicillin 1 g twice daily, clarithromycin 500 mg twice daily, and metronidazole 500 mg twice daily, followed by a 7-day dual regimen with pantoprazole 40 mg twice daily and amoxicillin 1 g twice daily) or a 14-day bismuth quadruple therapy (pantoprazole 40 mg twice daily, bismuth tripotassium dicitrate 120 mg, and tetracycline 500 mg four times daily for 14 days). All drugs are taken one hour before breakfast and dinner. Patients with peptic ulcers in initial endoscopy receive an additional 4-week pantoprazole therapy (40 mg orally once daily), while patients with symptomatic gastritis only take additional four-weeks of antacid.

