On recruitment, patients are requested to complete a standard record for a complete medical history and demographic data. Additionally, blood sampling for genotyping of *CYP2C19* is carried out. To assess eradication efficacy and status of ulcer healing, repeated endoscopy with rapid urease test, histological examination and culture is performed for peptic ulcer patients at the sixth week after the end of anti- *H. pylori* therapy. Urea breath test is conducted to assess *H. pylori* status in the subjects with gastritis and in peptic ulcer subjects who refuse follow-up endoscopy,. Eradication is defined as (1) negative results of both rapid urease test and histology, or (2) a negative result of urea breath test.

Finally, the eradication rates by both intention-to-treat and per-protocol analyses, adverse events and compliance will be compared between groups by chi-square test, and the host and bacterial factors influencing the efficacy of eradication therapy are assessed by multivariate analysis.

Statistical analysis

The primary outcome variable is eradication rate. The secondary outcome variables are the rate of adverse events and compliance. Chi-square test with or without Yates correction for continuity and Fisher's exact test are used when appropriate to compare the major outcomes between groups using the SPSS program (version 10.1, Chicago, Illinois, USA). A *P* value less than 0.05 is considered statistically significant.

Eradication rates are evaluated by ITT and per-protocol (PP) analyses. ITT analysis includes all randomized patients who have taken at least one dose of study medication. Patients whose infection status is unknown following treatment are considered treatment failures for the purposes of ITT analysis. The PP analysis excludes the patients with unknown *H. pylori* status following therapy and those with major protocol violations.

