To determine the independent factors affecting the treatment response, Host and bacterial parameters are analyzed by univariate analysis. These variables include the following: age (<60 or \geq 60 years), gender, history of smoking, history of alcohol consumption (<80 g/day or \geq 80 g/day), ingestion of coffee (<1 cup/day or \geq 1 cup/day), ingestion of tea ((<1 cup/day or \geq 1 cup/day), coexistence of a systemic disease (yes or no), previous history of peptic ulcer disease, endoscopic appearance (ulcer or gastritis), CYP2C19 polymorphism, drug compliance (good or poor), and antibiotic susceptibility. Those variables found to be significant by univariate analysis are subsequently assessed by a stepwise logistic regression method to identify independent factors for eradication outcome.

REFERENCES

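### The predictor analysis (aim 2) cuts age, alcohol, coffee and tea into two groups without a stated reason; if age acts roughly linearly, the cut at 60 gives up a material part of the information on age

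*Combined protocol and SAP*

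**What the plan says.** The last paragraph of the Statistical analysis section lists the variables to be examined as predictors of treatment response. Four that could be handled as quantities are coded as two groups:

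- Age: "These variables include the following: age (<60 or" 60 and above.
- Alcohol: "history of alcohol consumption (<80 g/day or" at or above that amount.
- Coffee: "ingestion of coffee (<1 cup/day or" one cup or more.
- Tea: "ingestion of tea ((<1 cup/day or" one cup or more.

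The coding decides what enters the model: "Those variables found to be significant by univariate analysis are subsequently assessed by a stepwise logistic regression method". The threshold is stated earlier in the section: "A *P* value less than 0.05 is considered statistically significant". The Study population section sets the total ("We will recruit 352 patients to the study") and a lower age limit ("they are adult patients aged ≥ 20 years"), with no upper limit and no expected age distribution. No passage explains any of the four cut-points or gives the expected number of patients on either side of them.

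**The concern.** Cutting age at 60 treats a patient of 59 like one of 25 and unlike one of 60. If risk changes gradually with age, that discards information. Because a variable must be significant on its own to reach the stepwise model, one weakened by its coding can be dropped before any adjustment.

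Aim 2 has little information to spare. Its effective sample size is the number of treatment failures, not 352. The Introduction cites 97.4% eradication by intention-to-treat for hybrid therapy, and above 90% in a multicentre trial. If this trial did as well, failures would number from about 352 × 0.026 = 9 to 352 × 0.10 = 35, set against about a dozen listed factors. These are literature rates, not design assumptions. The count could be higher, because unknown status is counted as failure in the intention-to-treat analysis.

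Alcohol raises a separate problem. Abstainers are grouped with everyone drinking up to 80 g/day, and the group above the cut may be very small.

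**Working it through.** The documents state no information loss, no power for aim 2, no age distribution and no drinking prevalence, so there is no plan figure to reproduce. From the documents: N = 352, the cut-points, and significance at 0.05 (sidedness not stated; taken as two-sided). Everything else below is assumed.

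**Information on age kept by the cut.** For a normally distributed age with a linear effect, let z = (60 − mean)/SD and p = 1 − Φ(z), the share aged 60 or over. The information kept is r² = φ(z)² / [p(1 − p)], and the loss is 1 − r².

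Worked example, mean 53 and SD 12: z = 7/12 = 0.583, φ(z) = 0.3365, p = 0.280, so r² = 0.1132/0.2016 = 0.562. The loss is 44%, like discarding 352 × 0.438 = 154 patients for this factor.

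| Assumed ages | Share ≥ 60 | r² | Loss | Equivalent patients lost |
|---|---|---|---|---|
| Normal, cut at the median | 50% | 0.637 | 36% | 128 |
| Normal, mean 58, SD 13 | 44% | 0.631 | 37% | 130 |
| Normal, mean 53, SD 12 | 28% | 0.562 | 44% | 154 |
| Normal, mean 50, SD 11 | 18% | 0.469 | 53% | 187 |
| Normal, mean 45, SD 12 | 11% | 0.353 | 65% | 228 |

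A median cut is the best case under the normal model. Truncating at age 20 lowers these losses slightly.

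For uniform ages the loss is 1 − 3p(1 − p):

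- Ages 20–80: p = 1/3, loss 33%.
- Ages 20–85: p = 0.385, loss 29%.
- Ages 30–80: p = 0.40, loss 28%.

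**Power for age.** Simulated trials of 352 patients, both arms pooled, with mean age 53, SD 12, ages truncated at 20, two-sided score tests at 0.05, and the overall failure rate held fixed. A range shows the spread between repeat simulations.

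| Assumed truth | Failures | Linear age | Cut at 60 |
|---|---|---|---|
| Linear, OR 1.65 per decade | 5% | 67% | 51–52% |
| Linear, OR 1.65 per decade | 8% | 83% | 68–69% |
| Linear, OR 1.3 per decade | 5% | 25% | 19% |
| Linear, OR 1.3 per decade | 8% | 36% | 26% |
| Step at 60, OR 3 | 5% | 43–44% | 62–63% |
| Step at 60, OR 3 | 8% | 57–58% | 78–79% |

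At the stronger linear effect the cut costs about 14–16 points. At the weaker one the gap is 10 points or less and power is poor either way. If risk truly steps at 60, the planned cut is the better analysis.

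Aim 2 refers to the outcomes of both regimens. If the analysis is run within each, the numbers are smaller and power is lower throughout. The percentage of information lost does not depend on N.

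**Alcohol.** Exposed patients = 352 × assumed prevalence: about 4 at 1%, 7 at 2%, 18 at 5% and 35 at 10%. With 5% failures, the expected failures among them are 0.2, 0.4, 0.9 and 1.8. The chance that none fails is 0.95ⁿ: 81%, 70%, 40% and 17%. With no failures in the exposed group, the ordinary logistic estimate is not finite.

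No loss can be calculated for coffee or tea, because the documents give nothing on their distribution.

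**The case against.** The strongest defence is that the cuts are fixed in advance, so they cannot be tuned to the data, and that two-group factors are easy to read. That stands as far as it goes, but prespecification does not recover lost information. A real threshold at 60 would favour the planned coding, as the step rows show. A curvature check would not reliably reveal it: in that scenario a quadratic test flagged curvature in only 6–8% of simulated trials, close to its false-positive rate.

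Four stronger readings are tempting, and the documents do not support them:

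- A reader might take 37–53% as the loss in this trial. It needs normal ages, a linear effect and about 18–44% of patients aged 60 or over. The documents give only the minimum age.
- A reader might infer that almost nobody will reach 80 g/day. No prevalence is given, and at 10% there would be about 35 such patients.
- A reader might infer that daily amounts of alcohol, coffee and tea are already recorded. The plan mentions only a standard record of medical history and demographic data, and the form might capture just the two categories.
- A reader might infer residual confounding by age in the other estimates. Nothing in the documents allows this to be sized. Age may also drop out at the univariate screen, which is a separate weakness that recoding does not cure.

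**Conclusion.** The point holds for age, and only for aim 2. The cut at 60 is unexplained and has no continuous alternative. Under a roughly linear effect, the loss was more than a quarter of the information on age under every distribution examined. How much more depends on an age distribution that the documents do not give. The cost in power is worthwhile to avoid at a strong age effect and small at a weak one, and its direction reverses if risk steps at 60.

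For alcohol, the supportable statement is that the size of the upper group is not given and may be too small to analyse. For coffee and tea, it is only that the cuts are unexplained. The comparison of eradication rates between regimens, and the secondary comparisons of adverse events and compliance, do not use these codings.

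**What to change.** In the Statistical analysis section:

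1. Enter age as a continuous variable, per 10 years, in both the univariate and the multivariable models.
2. Prespecify one flexible alternative (a 3-knot spline or a quadratic term), and report it alongside the linear result whatever its P value.
3. Keep the 60-year cut for descriptive tables.
4. Where the record form captures amounts of alcohol, coffee and tea, analyse them as amounts or as ordered categories tested for trend. For alcohol, look for a few very high values dominating a linear term. Ordered categories help only through the trend test, since a sparse top category stays sparse.
5. Where the form captures only the two categories, say so and report the number of patients and failures in each.

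The age change costs a sentence or two, since age should be available from the demographic record. For the other three variables the cost depends on the form. The downside is lower power for age if risk truly steps at 60, which a quadratic check may not detect.

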Institution/Department : Kaohsiung Veterans General Hospital

Principal Investigator (PI) : [name]

Research Project Title : Comparing the efficacy and impact on gastrointestinal microbiome of reverse hybrid therapy and bismuth quadruple therapy in *Helicobacter pylori* eradication

NCT Number : NCT02547038

Date of the document : 01 02 2019 (MM/DD/YYYY)

ABSTRACT

Background: With the rising prevalence of antimicrobial resistance, the failure rate of the standard triple therapy has declined to unacceptable level (<80%) worldwide. A 14-day hybrid therapy invented by our study group appears very promising in *H. pylori* eradication, achieving excellent eradication rates of 99% and 97% according to per-protocol and intention-to-treat analyses, respectively. Recently, we demonstrated that the eradication rate of reverse hybrid therapy was higher than that of standard triple therapy. However, whether reverse hybrid therapy achieves a higher eradication rate than bismuth quadruple therapy remained unanswered.

Aims: The aims of this randomized controlled trial are (1) to compare the efficacies of reverse hybrid therapy and bismuth quadruple therapy, (2) to investigate the host and bacterial factors predicting the treatment outcomes of the two eradication regimens.

Methods: Consecutive 352 *H. pylori*-infected subjects are randomly assigned to receive either a 14-day reverse hybrid therapy or a 14-day bismuth quadruple therapy. On recruitment, blood sampling for genotyping of *CYP2C19* is carried out, and antibiotic susceptibility of *H pylori* strains will be checked. Subjects are asked to return at the end of the 2nd week to assess drug compliance and adverse events. *H pylori* status will be re-assessed at week 6 after the end of anti-*H. pylori* therapy. Finally, the rates of eradication, adverse events and compliance will be compared between groups by chi-square test, and the host and bacterial factors influencing each efficacy of the regimen are assessed by multivariate analysis.

Introduction

Helicobacter pylori (*H. pylori*) infection is the principal cause of chronic gastritis, gastric ulcer,

duodenal ulcer, gastric adenocarcinoma and gastric mucosa-associated lymphoid tissue lymphoma.¹

In most international guidelines,²⁻⁴ 14-day standard triple therapy is still recommended as a choice

of treatment for the first-line therapy of *H. pylori* infection, especially in areas of low

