clarithromycin resistance ($\leq 15\%$). However, the eradication rates of standard triple therapy have declined to less than 80% in most countries because of the rising prevalence of clarithromycin resistance.⁵ Several strategies including bismuth-containing quadruple therapy and non-bismuth-containing quadruple therapy have therefore been proposed to increase the eradication rate.^{5,6}

In the Maastricht V/Florence Consensus Report,³ bismuth quadruple therapy is the treatment of choice for the first-line therapy of *H. pylori* infection in areas of high clarithromycin resistance ($> 15\%$) and an alternative in areas of low clarithromycin resistance. In the recent American College of Gastroenterology (ACG) guideline, it is also recommended as a first-line treatment for *H. pylori* infection.⁴ However, the complicated administration of bismuth quadruple therapy easily reduces the adherence of patients, and the complex therapy is associated with a high frequency of adverse events.^{7,8}

Hybrid therapy developed by Hsu et al. in 2011 consists of a dual therapy with a proton pump inhibitor (PPI) and amoxicillin for 7 days followed by a quadruple regimen with a PPI, amoxicillin, clarithromycin and metronidazole for 7 days.⁶ It achieved an eradication rate of 97.4% by intention-to-treat (ITT) analysis and 99.1% by per-protocol (PP) analysis in Taiwan.⁶ Subsequent randomized controlled trials demonstrated that 14-day hybrid therapies were comparable or more effective than 10-day sequential therapies.^{9,10} A recent large multicentre randomized controlled trial documented that 14-day hybrid and 14-day concomitant therapies had comparable efficacy in the treatment of *H. pylori* infection, and both could cure more than 90% of patients with *H. pylori* infections in areas of high clarithromycin and metronidazole resistance.¹¹ Currently, it is a recommended first-line

treatment choice in the ACG guideline⁴ and the Taiwan *Helicobacter pylori* Consensus Report.¹²

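### Drug compliance, measured after treatment, is a candidate in the stepwise model meant to find host and bacterial predictors; it can displace factors acting through adherence and, in an ITT fit, can pick up an artefact

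*Combined protocol and SAP*

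**What the plan says.** The aims, given in the Abstract and again in the Introduction, include "to investigate the host and bacterial factors predicting the treatment outcomes of the two eradication regimens". The last paragraph of Statistical analysis carries this out. It states that "Host and bacterial parameters are analyzed by univariate analysis" and lists twelve candidates, the last two being "drug compliance (good or poor), and antibiotic susceptibility". Candidates significant in the univariate step go into a stepwise logistic regression that decides which are independent.

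Elsewhere the document treats compliance as something that happens after randomisation:

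- Abstract, Methods: "Subjects are asked to return at the end of the 2nd week to assess drug compliance and adverse events". Both regimens last 14 days, so this visit falls at the end of treatment.
- Statistical analysis, outcomes: "The secondary outcome variables are the rate of adverse events and compliance".
- Introduction: "the complicated administration of bismuth quadruple therapy easily reduces the adherence of patients".

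On missing outcomes, Statistical analysis says "Patients whose infection status is unknown following treatment are considered treatment failures for the purposes of ITT analysis", and for the other set "The PP analysis excludes the patients with unknown *H. pylori* status following therapy and those with major protocol violations". The document does not say which set the regression uses, whether the arms are pooled, or how compliance is coded for someone who misses the week-2 visit. It plans no model without compliance.

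**The concern.** Compliance is neither a host nor a bacterial characteristic, and it is not known when treatment starts. It can lie on the path from a host factor such as age, alcohol use or systemic disease to cure. Putting it in the same model as those factors changes the question from whether a factor predicts eradication to whether it does so by a route other than adherence. The stepwise rule then turns that change into a decision: a factor whose effect runs through adherence may be left out of the reported list.

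A second, conditional problem comes from the ITT rule. If patients with unknown final status are more often recorded as poor compliers, counting them as failures links poor compliance to failure even when missed doses do no harm. Compliance could then be reported as a strong independent factor largely because of how missing outcomes were coded.

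What is at stake is the content of the aim-2 result. The comparison of eradication rates between arms does not use this model.

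**Working it through.** The plan gives no figure for the factor analysis, and no expected failure, dropout or compliance rate, so there is nothing of its own to reproduce. The structural point rests on the text; every rate below is an assumption for illustration.

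**1. Position of compliance in time.** Treatment lasts 14 days and compliance is recorded at the end of week 2. Final status is assessed six weeks after treatment ends. Compliance therefore falls after assignment and before outcome. The document compares it between arms and expects one regimen to lower it.

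**2. Loss of a mediated effect.** Assume cure of 94% in good and 50% in poor compliers, and a baseline factor that acts only by raising poor compliance from 3% to a share m.

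- Cure without the factor: 0.97 × 0.94 + 0.03 × 0.50 = 0.9268, odds 0.9268/0.0732 = 12.66.
- Cure with the factor at m = 20%: 0.80 × 0.94 + 0.20 × 0.50 = 0.852, odds 0.852/0.148 = 5.76.
- Total odds ratio for cure: 5.76/12.66 = 0.45.

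Within each compliance group cure is the same with or without the factor, so the odds ratio adjusted for compliance is 1.00.

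| Poor compliance with the factor (m) | OR without compliance in model | OR with compliance in model |
|---|---|---|
| 5% | 0.88 | 1.00 |
| 10% | 0.68 | 1.00 |
| 15% | 0.55 | 1.00 |
| 20% | 0.45 | 1.00 |

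Weighted logistic regression on exact cell probabilities, with the factor present in 30% of patients, covers two further cases:

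- Direct effect (OR 0.50) plus the mediated effect at m = 20%: OR 0.27 without compliance, 0.50 with it.
- Direct effect only (OR 0.25), unrelated to compliance (5% poor in both groups, cure 95% in good and 50% in poor compliers without the factor): OR 0.30 without compliance, 0.25 with it. This factor is not absorbed.

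**3. Artefact from the ITT rule.** Let u be the share with unknown status and q the share of those recorded as poor compliers. Among assessed patients assume 4% poor compliance and 7% failure whatever the compliance, so the true odds ratio is 1.

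- Poor share: P = uq + (1 − u) × 0.04
- Failure in poor compliers: [uq + (1 − u) × 0.04 × 0.07] / P
- Failure in good compliers: [u(1 − q) + (1 − u) × 0.96 × 0.07] / (1 − P)

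For u = 0.05 and q = 0.50: P = 0.025 + 0.038 = 0.063. Failure in poor compliers is 0.02766/0.063 = 0.439, and in good compliers 0.08884/0.937 = 0.095. The odds ratio is 0.783/0.105 = 7.5.

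| u | q | Failure, poor | Failure, good | OR for failure |
|---|---|---|---|---|
| 5% | 4% | 11.7% | 11.7% | 1.0 |
| 5% | 10% | 17.8% | 11.4% | 1.7 |
| 5% | 30% | 33.3% | 10.4% | 4.3 |
| 5% | 50% | 43.9% | 9.5% | 7.5 |
| 3% | 50% | 32.9% | 8.5% | 5.3 |
| 2% | 50% | 25.9% | 8.0% | 4.0 |

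With unknown status excluded, failure is 7% in both groups and the odds ratio is 1.0 throughout.

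**4. Pooled or per-arm fit.** The Abstract can be read as one model per regimen. In that case compliance cannot stand in for the regimen, but it is still a post-treatment variable. If the arms are pooled, it can also stand in for the regimen, because treatment arm is not among the candidates.

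**The case against.** The regression paragraph states its goal as finding what independently affects treatment response, and compliance plausibly does. For explaining why eradication fails, compliance is a natural variable, and an estimate adjusted for it is a legitimate, different quantity. A mediated factor does not disappear either, because its total association is estimated in the univariate step. All of this stands. It is a reason to keep the compliance result in view, but not to let compliance decide which host and bacterial factors are called independent, since that is what the aim is limited to.

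The other side also limits the size of the problem, and a reader might infer more than the documents support in four ways:

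- *That compliance must predict failure by construction.* This needs the ITT set, which the plan does not name for the regression, and more unknown status among poor compliers whose compliance was recorded. A patient who leaves before the week-2 visit may have no compliance record, and one lost after it may have complied well. In the PP set the mechanism is absent. If poor compliance counts as a major violation, which is not defined, the variable would hardly vary there.
- *That baseline predictors in general are absorbed.* Only those acting through adherence are. Nothing in the document gives CYP2C19 genotype or antibiotic susceptibility such a path.
- *That the artefact is always large.* The high odds ratios come from assuming that 30% to 50% of unknown-status patients are recorded as poor compliers. At 10% the figure is 1.7 and at 4% it is 1.0.
- *That the aim is to choose which patients each regimen suits.* The document does not say this; it speaks only of factors predicting outcome.

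**Conclusion.** The concern holds in a limited form. The text establishes that a post-treatment variable, itself a secondary outcome and expected to depend on the regimen, is a candidate in the model for host and bacterial factors, and that no model without it is planned. Followed as written, the stepwise rule can drop or weaken a factor that acts through adherence: in the illustration, a total odds ratio of 0.45 to 0.88 becomes 1.00.

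The link to failure through missing outcomes is a further possibility that depends on the analysis set and on how compliance is recorded in patients with unknown status. Under the stated assumptions with 5% unknown, its size runs from none (OR 1.0) to about 7.5, and it is zero when unknown status is excluded. The document gives no rates that would place this trial within that range.

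The primary eradication comparison and the between-arm comparison of compliance are not affected. The point is worth acting on because it concerns a stated aim and costs almost nothing to correct.

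**What to change.** In the last paragraph of Statistical analysis:

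1. Restrict the aim-2 predictor model to variables known before the first dose, by removing drug compliance from that candidate list.
2. Name the analysis set for the regression, and state whether it is fitted per arm or pooled with treatment arm included.
3. Report eradication by compliance separately, by arm, in patients whose status six weeks after treatment is known, labelled as a post-treatment association. A secondary model that adds compliance to the baseline model would serve equally well and keeps the adjusted estimate.

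The cost is one deletion, a sentence or two of specification, and one extra table or model. No new data and no change in sample size are needed. The small downside is that compliance no longer appears in the main list of independent factors, though its association with eradication is still shown.

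### Aim 2: univariate screening of 12 factors followed by stepwise logistic regression will often name an independent factor when none exists, and nothing in the plan controls this

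*Combined protocol and SAP*

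**What the plan says.** The Introduction gives the second of two aims as "to investigate the host and bacterial factors predicting the treatment outcomes of the two eradication regimens". The last paragraph of Statistical analysis lists 12 candidates: age, gender, smoking, alcohol, coffee, tea, systemic disease, previous ulcer disease, endoscopic appearance, CYP2C19 polymorphism, and finally "drug compliance (good or poor), and antibiotic susceptibility". Each is analysed univariately. Then: "Those variables found to be significant by univariate analysis are subsequently assessed by a stepwise logistic regression method".

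That paragraph says only that a variable must be significant. The sole threshold in the document is the general P<0.05 earlier in the same section. That section also names chi-square with or without Yates correction and Fisher's exact test, but for comparing the major outcomes between groups. No test is named for the factor screen, and no entry or removal criteria for the stepwise model.

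On whether arms are pooled, the Abstract says "the host and bacterial factors influencing each efficacy of the regimen are assessed by multivariate analysis", while the end of Randomization and treatment says "the host and bacterial factors influencing the efficacy of eradication therapy are assessed by multivariate analysis". Treatment arm is not a listed variable. ITT and PP sets are defined for eradication rates, and neither is assigned to the factor analysis. Under ITT, "Patients whose infection status is unknown following treatment are considered treatment failures". The PP set drops patients with unknown *H. pylori* "status following therapy and those with major protocol violations".

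**The concern.** Screening many candidates at 0.05 and passing the survivors to a stepwise model applies the same noise twice. A factor that passes by chance has, by construction, a large apparent effect in these data, so the stepwise stage seldom removes it. The reported odds ratio is conditional on having looked large. The problem is worst when there are few events, and an effective eradication regimen leaves few failures.

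What is at stake is a published list of independent predictors that would not replicate, under an aim given equal billing with the efficacy comparison.

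Drug compliance raises a separate issue. It is observed after randomisation, so it is not a baseline predictor. If the ITT outcome were used, patients with unknown status would be coded as failures; if those patients also comply poorly, compliance becomes linked to failure by the coding rule alone.

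The plan also says that "antibiotic susceptibility of *H pylori* strains will be checked", but gives no rule for patients without a result.

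**Working it through.** The plan states no error rate or power for the factor analysis, so there is no figure of its own to reproduce.

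**Inputs.** From the documents: N = 352; 12 listed factors; alpha 0.05. Assumed: 1:1 allocation (176 per arm); eradication 97.4% and 90% (the Introduction quotes such rates for other regimens, not as planning values) and 80%; 12 independent binary factors with prevalence 5-50%; no factor has any effect.

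**Failures available** (N × failure rate, then divided by 12):
- All 352: 352 × 0.026 = 9.2 (0.76 per candidate); 352 × 0.10 = 35.2 (2.93); 352 × 0.20 = 70.4 (5.87).
- One arm of 176: 4.6 (0.38), 17.6 (1.47), 35.2 (2.93).

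**Screen alone, nominal.** 1 − 0.95^12 = 46.0% chance of at least one false pass, with 12 × 0.05 = 0.60 expected. If susceptibility is tested separately for four antibiotics, the list becomes 12 − 1 + 4 = 15 and the chance is 1 − 0.95^15 = 53.7%. Sparse failures make the actual tests more conservative than this, so simulation is needed.

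**Screen plus stepwise, simulated under the null.** Screen at P<0.05, then backward logistic selection by likelihood ratio at P<0.05. The first two rows in each block used 3,000 trials per setting; the Yates rows used 800 to 1,000. Entries are the percentage of trials with at least one false factor retained.

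| Screening test | 97.4% | 90% | 80% |
|---|---|---|---|
| *Pooled, 352* | | | |
| Uncorrected chi-square | 34.0 | 40.4 | 42.8 |
| Fisher if an expected count <5, else uncorrected | 26.9 | 39.5 | 42.5 |
| Fisher if an expected count <5, else Yates | about 27 | about 28 | about 36 |
| *One arm, 176 (q)* | | | |
| Uncorrected chi-square | 30.9 | 39.2 | 42.2 |
| Fisher if <5, else uncorrected | 20.0 | 37.1 | 42.5 |
| Fisher if <5, else Yates | about 20 | about 28 | about 30 |

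At least one of two arms is 1 − (1 − q)²:
- Uncorrected: 52.3%, 63.0%, 66.6%.
- Fisher, else uncorrected: 36.0%, 60.4%, 66.9%.
- Fisher, else Yates: about 36%, 48%, 51%.

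Repeat runs moved these by a few points, as expected: the 95% simulation error at 1,000 trials is about 1.96 × √(0.4 × 0.6 / 1000) = 3 points. Over all runs and tests the ranges are:
- 97.4-90% eradication: about 27-41% pooled and 35-65% for at least one arm.
- 80% eradication: about 36-46% pooled and 52-68% for at least one arm.

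Forward instead of backward selection (2,000 trials, pooled, 90%) gave a false pass at the screen in 42.0% of trials and a false factor retained in 39.1%. The stepwise stage therefore removes little.

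**Size of retained odds ratios (true value 1.0), pooled.** At about 9, 35 and 70 failures, the median is about 7, 2.6 and 2.1 after ORs below 1 are inverted, so that both directions count as distance from 1. As retained, without inversion, it is about 5, 2.1 and 1.8.

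**Compliance under ITT, illustration only.** Assume 3% unknown, 5% true failure among the rest, 4% poor compliance among the rest, and 20% poor compliance among those lost. Coded failures are 0.03 + 0.97 × 0.05 = 0.0785 of patients. Poor compliers among them are (0.03 × 0.20 + 0.0485 × 0.04)/0.0785 = 10.1%. The OR is (0.1011/0.8989)/(0.04/0.96) = 2.7, although compliance has no effect on cure. With 4% poor compliers among the lost, the OR is 1.0.

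**The case against.** The plan deserves credit for fixing its candidate list in advance, with cut-points for age, alcohol, coffee and tea, which limits data-driven searching. Factor analysis is neither the primary nor a secondary outcome variable. The plan also allows Yates correction, which lowers pooled false selection at 90% eradication from about 40% to about 28%. All of this stands. It narrows the size of the problem, but more than a quarter of null trials still name a factor.

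Several stronger readings are tempting but not supported:
- **That false selection must be around 40% pooled, or above 60% for at least one arm.** Those values belong to the more liberal tests at the higher failure rates. The plan does not fix the screening test.
- **That pooling will dilute a clarithromycin-resistance effect.** Clarithromycin is given in one arm only, so dilution would follow if arms were pooled without an interaction. The plan does not say they are pooled, and the aim and the Abstract lean towards one model per regimen.
- **That compliance will appear as a spurious predictor.** This needs the ITT outcome and worse compliance among lost patients; the plan specifies neither. Conversely, a PP analysis might remove poor compliers, but major violations are not defined.
- **That the efficacy comparison is compromised.** It is a separate analysis.

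Arm handling, analysis set and missing susceptibility are thus missing detail, to be settled in the wording. They are not demonstrated biases.

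**Conclusion.** The concern holds for the selection rule and should be corrected before the factor analysis is run. Followed as written, the rule gives unreliable answers to a stated aim: under the null it names at least one factor in roughly three to four of every ten trials if arms are pooled, and more often across two per-arm models, with exaggerated odds ratios attached. The plan contains nothing that would warn a reader of this.

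Confidence is high on the mechanism and moderate on the figures. They rest on assumed eradication rates, 1:1 allocation, independent binary factors with no true effect, and P<0.05 carried over from the general rule; correlation between factors would lower them.

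**What to change.** Replace the last paragraph of Statistical analysis with the following:

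1. Drop the univariate gate and the stepwise selection. For all 12 factors, show eradication by arm as counts with exact confidence intervals and no P values.
2. In patients with known *H. pylori* status, fit one prespecified penalised logistic model (for example Firth). Include arm and a short list of baseline factors from the plan's own list, with reasons written in advance; CYP2C19 and antibiotic resistance should be among them. For a drug given in only one arm, either let the resistance effect differ by arm or estimate it within the arm that receives the drug, using the same rule for every drug. State how patients without a susceptibility result are handled. Keep compliance descriptive.
3. Report estimates with confidence intervals, label every factor finding exploratory, and do not use the term independent factor.

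Before resistance is assigned to the bismuth arm, Randomization and treatment must be reconciled: it lists three drugs under a regimen called quadruple.

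Cost: SAP wording and software beyond the SPSS 10.1 named in the plan; no new data. Fewer factors are modelled, and intervals will be wide when failures are few. As an example, with 3% unknown status (assumed) about 341 patients remain. A four-term model would then have 341 × 0.026 / 4 = 2.2 failures per term at 97.4% eradication and 341 × 0.10 / 4 = 8.5 at 90%. At the sparse end, the tables in item 1 carry most of the information.
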